#### **Study duration**

The expected duration of the study is 1 year. The relevant dates are data collected from December 1st, 2020 to December 1st, 2021.

# **Target population**

Adult patients who as part of their routine clinical care receive focused TEE in the emergency department of intensive care setting. Children (age under 18 years) will not be eligible for inclusion in this study.

### Subjects enrolled by Penn Researchers

### Subjects enrolled by Collaborating Researchers

N/A

#### **Vulnerable Populations\***

None of the above populations are included in the research study

### Subject recruitment\*

Not applicable

#### Subject compensation\*

No

#### Procedures

There are no interventions or procedures in this study. As part of this study, we are not proposing any manipulation to the subject's clinical environment, therefore any procedures or surgical interventions that take place during the clinical encounter in which TEE is being performed, are being performed as part of standard clinical care and in the interest of the patient rather than for study purposes.

We will be entering previously described clinical data into REDCap from EPIC patient charts. The TEE ultrasound clips that are routinely stored for quality assurance will be reviewed, analyzed, and qualitative data will be extracted. All of the data will be analyzed retrospectively from standard of care procedures. Follow-up, beyond hospital discharge of subjects will not occur.

### Deception

No

#### **Analysis Plan**

Baseline and demographic characteristics will be summarized by standard descriptive statistics (including mean and standard deviation for continuous variables such as age and standard percentages for categorical variables such as gender). Continuous variables will be analyzed using Student's t-test, categorical data using Chi-square. Descriptive statistics will be presented as a mean with standard deviation, or as a median with an interquartile range. Differences in patient characteristics will be analyzed using  $\chi^2$  testing, Student's t-test, or the Mann-Whitney U test, as appropriate. We will provide frequencies with their binomial 95% confidence intervals for descriptive purposes. For bivariate or multivariable analyses, we will use logistic regression, ANOVA, or chi-squared testing, as appropriate. Statistical methods will be performed in statistical software (STATA).

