# **Overall objectives**

The primary objective of this study is to determine the **clinical impact** and **safety** of transesophageal echocardiography (TEE) performed during the evaluation of critically-ill patients in the **emergency department** and **intensive care settings**.

The secondary objective(s) of this study are to **characterize the use of this imaging modality** in the subsets of critically-ill patients in **shock and cardiac arrest**; including but not limited to; description of the frequency of studies, clinical indications, clinician characteristics, echocardiography findings, timing of studies, procedure-related complications and patient outcomes.

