While the above-mentioned studies have provided some promising data on the utility of this emerging modality, to date only small single center and retrospective studies have evaluated the clinical impact of focused TEE in resuscitative settings. Furthermore, no studies have investigated the safety of this imaging modality, specifically in the population of emergency department patients. The proposed study has the potential to substantially improve our understanding of the clinical impact and the safety of TEE in emergency and critical care applications.

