# **Study Design**

### Design

We plan to conduct a prospective observational study involving a convenient sample of patients receiving a TEE as part of their clinical care in emergency department (ED) and intensive care unit (ICU) settings. The study will enroll adult patients receiving focused TEE as part of their routine care for the most common clinical indications of focused TEE in critical care patients in ED and ICU settings including: 1. Evaluation of intra-arrest and post cardiac arrest in inhospital (IHCA) and out-of-hospital cardiac arrest (OHCA), 2. Evaluation of patients in shock, 3. Hemodynamic monitoring, and 4. Procedural guidance.

Data will be collected from the patients' electronic medical record (EMR) and EMS run-sheets in the case of OHCA cases. Transesophageal echocardiography (TEE) images routinely recorded for quality assurance and as part of standard clinical care, will be collected. Patients will be

enrolled in the study by clinicians participating from their care who are involved in the performance of TEE. Following identification of eligibility criteria by the enrolling clinician, a RedCap data collection instrument will be used to prospectively gather basic demographics, and clinical data, including the indication for the TEE (i.e. including intra-arrest or post arrest, evaluation of shock, hemodynamic monitoring or procedural guidance), operator findings on the TEE, probe insertion procedure details, TEE views obtained during the study, clinician's interpretation of the images, change in management (if any) as a result of the information provided by TEE. Procedure-related immediate complications, and outcomes when indicated.

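### Does naming only chi-square for categorical data, with no small-count test, put the comparison of rare TEE complications at risk of false positives?

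*Protocol*

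**What the plan says.** The protocol's Analysis Plan has three sentences on tests.

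- The first is general and unqualified: "Continuous variables will be analyzed using Student's t-test, categorical data using Chi-square".
- The second concerns differences in patient characteristics. It lists chi-square, the t-test "or the Mann-Whitney U test, as appropriate".
- The third reads "For bivariate or multivariable analyses, we will use logistic regression, ANOVA, or chi-squared testing, as appropriate".

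Between the second and third stands the rule for proportions: "We will provide frequencies with their binomial 95% confidence intervals for descriptive purposes".

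Safety is half of the primary objective in Overall objectives. The secondary objectives there describe how TEE is used, down to "timing of studies, procedure-related complications and patient outcomes". The Design section lists among the data collected "Procedure-related immediate complications, and outcomes when indicated", and its four indications end with "3. Hemodynamic monitoring, and 4. Procedural guidance". The Sample size section calls the study descriptive and expects about 100 TEEs in a year.

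The protocol gives no complication rate, group sizes, significance level or hypothesis about complications.

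**The concern.** Chi-square relies on a large-sample approximation that fails when expected counts are small. The Analysis Plan gives continuous data a fallback (Mann-Whitney) but names no counterpart for sparse categorical data. Logistic regression is named, but it does not help when a group has no events, because the ordinary maximum-likelihood estimate for that group then does not exist.

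Sparse tables are easy to foresee. If 1-3% of 100 TEEs have a complication, there are one to three events to spread over two settings or four indications. One chance event in a small group could then be reported as a significant safety difference. That would matter, because the Background says "no studies have investigated the safety of this imaging modality, specifically in the population of emergency department patients" and the protocol hopes its results may inform guidelines.

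**Working it through.** **Inputs.** From the protocol: N of about 100 (Sample size) and chi-square for categorical data (Analysis Plan). Assumed, because the protocol is silent: complication rate 1-5%, two-sided 5% level, the group splits, and a between-group test of complications. The protocol states no error rate, so there is no figure of its own to reproduce.

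**Step 1: one event.** With a single event, in a group of m out of N, and none elsewhere, the uncorrected Pearson statistic is N(N - m)/((N - 1)m). For two groups the 5% critical value is 3.84.

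- m = 20: 100 × 80/(99 × 20) = 4.04, p = 0.044. Fisher's exact test gives 20/100 = 0.20.
- m = 21: 100 × 79/(99 × 21) = 3.80, p = 0.051. Not significant.

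**Step 2: true size at fixed splits.** Enumerate all tables with equal true rates, add the probabilities of those that Pearson rejects, and count tables without events as no rejection. For N = 100:

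| Split | 1% | 2% | 3% | 5% |
|---|---|---|---|---|
| 80/20 | 8.8% | 8.7% | 7.2% | 4.7% |
| 60/20/10/10 | 9.4% | 9.8% | 8.8% | 6.7% |
| 79/21 | 1.5% | 3.7% | 4.8% | 4.7% |
| 90/10 | 4.1% | 4.3% | 4.5% | 5.4% |
| 70/30 | 1.9% | 3.8% | 4.6% | 4.9% |
| 50/50 | 0.2% | 1.3% | 2.8% | 4.3% |
| 25/25/25/25 | 0.4% | 1.4% | 2.3% | 3.2% |

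The inflation is real in the first two rows. Imbalance alone does not produce it: 90/10 and 70/30 stay near or below 5%.

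**Step 3: why 80/20 and 79/21 differ so much.** At a 1% rate the chance of exactly one event is 100 × 0.01 × 0.99^99 = 0.370. The chance that it falls in the group of 20 is 0.20, and 0.370 × 0.20 = 7.4%. So 7.4 of the 8.8 points come from that single table, which just crosses the critical value at m = 20 and fails to cross it at m = 21. The 80/20 example sits on the least favourable integer.

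**Step 4: group sizes left to chance.** The Design section describes a convenience sample, so no group size is fixed in advance. Drawing group membership at random with the expected shares, at rates of 1/2/3/5%:

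- expected 80/20: 4.7/5.3/5.0/4.4%
- expected 60/20/10/10: about 6-7%
- expected 50/30/10/10: about 5.3-6.2%
- expected 70/15/10/5: 7.0-8.4%

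For two groups almost nothing is left. For four unequal groups a moderate excess remains, largest when one group is expected to hold only about five patients.

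**Step 5: what the protocol does with complications.** It reports frequencies with binomial 95% intervals. If these are computed exactly (Clopper-Pearson), the results are 0/100: 0-3.6%; 1/100: 0.03-5.4%; 3/100: 0.6-8.5%. No chi-square test enters them.

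**Step 6: what an exact test would change.** Fisher's test at 80/20 has a true size of 0.8-1.9% over rates of 1-5%, and at 50/50 of 0.0-0.7%. It removes the inflation but is very conservative. With one to three expected events, no test can usefully detect a group difference.

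**The case for a change.** The best argument for the concern is that this is a choice made, not a detail omitted. The first test sentence assigns categorical data to chi-square without qualification. Leaving the choice open in the later sentences can only mean choosing among the methods listed, and none of those suits small counts. An analysis plan that added an exact test would depart from that sentence. The protocol does foresee bivariate analyses, and with four unequal indications the true size can come close to 10%.

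Part of this stands. No small-count method is named, logistic regression is not one, and the calculated error rates are correct for the splits shown. But the first sentence names a default. Nothing in it excludes an exact version where the approximation fails, and the two sentences that follow leave room for judgement. The only comparison tied to named variables concerns patient characteristics. The sentence on bivariate and multivariable analyses names no outcome. To reach an inflated error, the reader must add the comparison, the 5% level, a rate of 1-3% and one of certain splits.

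**Conclusion.** The concern does not hold. The excess error, about 7-10% against a nominal 5%, belongs to an analysis the protocol does not plan and to inputs it does not give. Complications as planned are counts with binomial intervals in a study that calls itself descriptive, and those results are unaffected. Even if complications were compared, the excess occurs only at particular group sizes. It largely vanishes for an expected 80/20 split once sizes are random (4.4-5.3%), though 7.0-8.4% remains for an expected 70/15/10/5.

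A fallback for sparse cells is routine statistical analysis plan content, and that plan is not shown, so its absence from the protocol is no error. This conclusion assumes that complications are reported descriptively, as the Analysis Plan and Sample size sections indicate. A formal test of complications between small groups would change that.

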Minimal patient demographic information to be collected including: age, gender, and BMI. In the case of cardiac arrests, when applicable the following information will be collected: if the arrest was witnessed, location of arrest, if bystander CPR was performed, will be obtained from the EMR and EMS run sheets. Identification of certain disease states in the medical history patients such as coronary artery disease, congestive heart failure, chronic kidney disease, diabetes mellitus, hypertension, previous STEMI, ventricular assist device, and implantable cardioverterdefibrillator will also be obtained from the EMR and prospectively entered to the RedCap data form. For cases of OHCA, data collection will also include an analysis of pre-hospital care to examine the following factors (Ustein Cardiac Arrest Variables); estimated time of arrest, response time, EMS interventions (chest compressions, defibrillation, airway procedures, dosing and timing of drug administration). For all cardiac arrest cases, information collected will also include time of arrest, ED arrival time in case of OHCA, time to first image of TEE, time of first rhythm, and times and type of intervention (mechanical CPR, arterial line, epi administration, etc.) The study of patient outcomes will be specific to the clinical indication and will include ROSC, survival to hospitalization and discharge in OHCA. In cardiac arrest cases, additional factors pertaining CPR physiology will be examined.

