#### Sample size:

Consistent with the descriptive nature of this study, our intention is to capture as many TEEs as possible within those performed across the clinical indications of interest for this study. Based on

prior research and Quality Assurance data, over the period of one year, we estimate a total of approximately 100 studies to be performed and analyzed as part of this study.

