#### **Potential Study Risks**

Given the design as an observational protocol, there are no interventions as part of this study. As explained before, all the interventions such as procedures occurring during this protocol are the standard clinical practice and their use will be directed by the treating physicians as part of the standard care.

Radioisotopes/radiation-producing machines (e.g., X-rays, CT scans, fluoroscopy) and associated risks: No radioisotopes or radiation-producing machines will be used during the protocol.

Physical well-being: Participation in this study will not incur any additional risk to subjects' physical well being beyond what would be experienced during standard care. Psychological well-being: Participation in this study will not incur any additional risk to subjects' psychological well being beyond what would be experienced during standard care. Economic well-being. Participation in this study will not incur any additional risk to subjects' economic well being beyond what would be experienced during standard care. Social well-being. Participation in this study will not incur any additional risk to subjects' economic well being beyond what would be experienced during standard care. Social well-being. Participation in this study will not incur any additional risk to subjects' social well being beyond what would be experienced during standard care. Social well being beyond what would be experienced during standard care. Social well being beyond what would be experienced during standard care. Social well being beyond what would be experienced during standard care. Although the risk of mortality in our patient population is high (approximately 90%), the risk of the observations made in this study are minimal as all observations are currently being recorded as part of standard of care. All laptops, desktops, and mobile devices used to access, transmit, or store Prohibited or Restricted Data as defined under the Data Classification Guidelines are encrypted. We will make sure that any new device used in this study will be encrypted prior to use.

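### Does the planned logistic regression break down because only about 10 survivors are expected?

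*Protocol*

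**What the plan says.** The Analysis Plan in the Protocol is a general list of methods. On modelling it has one sentence: "For bivariate or multivariable analyses, we will use logistic regression, ANOVA, or chi-squared testing, as appropriate". It ties no method to an outcome, lists no covariates and does not say how a logistic model would be estimated. The same section promises frequencies with binomial 95% confidence intervals.

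The other relevant statements are spread over the Protocol:

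- Sample size: "we estimate a total of approximately 100 studies to be performed and analyzed as part of this study". The section calls the study descriptive and gives no power calculation.
- Potential Study Risks: "Although the risk of mortality in our patient population is high (approximately 90" (a percentage), with no time point and no breakdown by indication.
- Study Design, Design: outcomes depend on the indication and "will include ROSC, survival to hospitalization and discharge in OHCA". The enrolling clinician also records "change in management (if any) as a result of the information provided by TEE".
- The same section lists what will be recorded: "Minimal patient demographic information to be collected including: age, gender, and BMI"; a medical history that includes "coronary artery disease, congestive heart failure, chronic kidney disease, diabetes mellitus, hypertension, previous STEMI, ventricular assist device" and implantable defibrillator; and, for cardiac arrests, witnessed status, location and bystander CPR.
- Overall objectives: clinical impact and safety are primary. Patient outcomes appear among the features to be described under the secondary objective.

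**The concern.** Read together, these statements suggest a known trap. Survival to discharge is a named binary outcome, and logistic regression is the only listed method that gives an adjusted analysis of a binary outcome. The Protocol's own figures leave about 10 survivors, and it records at least 14 patient and arrest variables. Maximum-likelihood logistic regression with less than one event per covariate is biased away from the null and often separates, so that no finite estimate exists. If such a model were fitted, exaggerated odds ratios could be reported as predictors of survival after TEE. The section on potential benefits hopes that the results will inform guidelines, so the error would matter.

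**Working it through.** **Inputs from the Protocol.** About 100 studies (Sample size) and about 90% mortality (Potential Study Risks). The 100 is a feasibility estimate without alpha, power or effect size, so there is no calculation to reproduce.

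**Expected survivors.** 100 × (1 − 0.90) = 10, with a binomial 95% range of 5 to 16. At 85% or 95% mortality the figure is 15 or 5. The arithmetic behind the concern is correct.

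**Events per variable if everything recorded were modelled.** 8 history items + 3 demographics + 3 arrest items = 14, and 10 / 14 = 0.71. Without the arrest items, 10 / 11 = 0.91.

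**What ordinary logistic regression does with about 10 events.** Two simulations were run with 1,500 data sets per setting, N = 100, about 10% survival and a true odds ratio of 2. Simulation A used binary covariates with 35% prevalence, one with an effect and the rest null. Simulation B mixed binary and continuous covariates, all with effects. These covariate settings and the odds ratio are assumptions. Each cell gives the geometric mean odds ratio among fits that converged, then the share that separated or did not converge.

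| Covariates | A | B |
|---|---|---|
| 1 | 2.02; 0.9% | 2.05; 0.9% |
| 2 | not run | 2.23; 0.9% |
| 3 | 2.13; 6.0% | 2.05; 2.7% |
| 5 | not run | 2.22; 3.9% |
| 6 | 2.19; 13.7% | not run |
| 8 | not run | 2.40; 7.3% |
| 10 | 2.41; 19.8% | 2.70; 15.6% |
| 14 | 2.65; 29.3% | not run |

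With one to three covariates the average stays between 2.02 and 2.23, and failures between 0.9% and 6.0%. The main weakness there is imprecision: in B the upper 95% limit is a median 16 to 19 times the lower. With 10 covariates that ratio is 60. For an outcome with 40% frequency (assumed) at N = 100, three to eight covariates give 2.11 to 2.22 with no failures.

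**Does the Protocol plan the harmful model?** Set side by side, the sections do not support that reading:

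- The Analysis Plan sentence covers bivariate and multivariable analyses alike and leaves the choice open. No section links it to survival. It could equally serve change in management or ROSC, for which no rates are given.
- The 14 variables are listed as data to collect. None is proposed for a model.
- Three of them exist only for cardiac arrests. A 14-covariate model on all 100 studies could not be fitted unless every patient had arrested, yet the design also enrols for shock, hemodynamic monitoring and procedural guidance.
- For sparse outcomes the plan already offers a suitable summary. With 10 of 100 surviving, an exact binomial 95% interval runs from 4.9% to 17.6%.

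**The case for a change.** The strongest counter-argument is that leaving the choice open does not help when the list holds nothing suitable. ANOVA and chi-squared give no adjusted analysis of a binary outcome, and no exact or penalised method is named. Chi-squared is strained too: with 10 survivors and a covariate of 35% prevalence (assumed), one expected cell count is 10 × 0.35 = 3.5. Survival is specified for OHCA, which is only part of the sample. If 30 to 50 of the 100 are OHCA (assumed) with the same 10% survival, 3 to 5 survivors remain. At N = 50, simulation B fails in 14% of data sets with one covariate, 23% with three and 77% with ten. Repeat studies in one patient would lower the counts further.

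Part of this stands. A model with many covariates, or any adjusted model on about five survivors, would be unreliable. Firth's penalised likelihood would do better at N = 100, averaging 1.96 to 2.10 across both simulations. Even small models at N = 100 are noisy: in B, with one to three covariates, 19% to 21% of data sets give an odds ratio above 4 or fail.

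It does not show an error in the Protocol. Logistic regression is named as a type of model, and penalised and exact versions are forms of it. The noise in small models is imprecision, which the confidence intervals would show. The OHCA share is not stated, and the 90% is a remark in the risk section about the whole population. Above all, the argument supposes an adjusted survival model that the document does not announce.

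**Conclusion.** The concern does not hold. The figure of about 10 survivors is a fair inference, and a large survival model on that basis would be poor, but the Protocol neither plans nor implies one. At N = 100, models with one to three covariates show little to modest inflation (2.02 to 2.23 against a true 2) and fail in at most 6.0% of data sets. Averages of 2.4 or more appear only with eight or more covariates, and failure above 10% only with six or more. Otherwise the harm depends on an OHCA subset of assumed size. Complications cannot be added to the argument, because the Protocol gives no rate for them.

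What remains is that no covariate limit or small-sample estimator is stated for an analysis that may never be done. That is commonly settled in an SAP, which may exist but is not shown, so its absence from the Protocol is not a fault. The conclusion rests on reading the Analysis Plan as a general list within a descriptive study, and on the simulation assumptions given above. It would change if a plan were produced that fits survival on many of the recorded variables, or fits an adjusted model to a handful of OHCA survivors.
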